## 3.4 Statistical Interim analyses

No formal interim analysis was planned for the primary endpoints. However due to lower enrollment than expected after 8 months of recruitment, we planned an ad-hoc sample size recalculation to calculate the expected power of the study based on updated parameters. The power will be re-calculated using the actual clinical failure data from the control arm, adjusting the upper limit of the non-inferiority margin based on the risk ratio of 1.3, and taking into the actual enrollment numbers extrapolated up to mid-October 2022 (which corresponds to the end of 6 months of enrollment in all health facilities). All the other sample size calculation parameters will remain the same (see above)). The following approaches will therefore be undertaken based on the calculated power:

- If the updated sample size calculation finds a power of  $\geq 80\%$ , then the study will end as planned mid-October 2022.
- If the updated sample size calculation finds a power of  $< 80\%$  we will prolong the study, or increase the number of health facilities as required.

The sample size recalculation will be performed by an independent statistician, who will share the results of the updated sample size to the study investigators. To avoid implementation bias, the clinical failure proportion in the control arm will not be shared.

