## 3.3 Sample size

The primary analysis will evaluate whether the use of ePOCT+ for case management of sick children in PHC facilities 1) results in similar clinical cure at day 7 (non-inferiority analysis), as compared to routine care and 2) decreased antibiotic prescriptions (superiority analysis) at the initial consultation. The sample size was calculated for testing the non-inferiority of the clinical cure outcome, which will require a much larger sample size due to the rareness of clinical failure. In addition, the testing of differences in antibiotic prescription is conditional on satisfying non-inferiority in the clinical outcome. Assuming a failure rate (not being cured at day 7) of 3% in the control arm (corresponding to a 97% clinical cure rate), based on previous studies, the acceptable non-inferiority margin will be a risk ratio of 1.3. This corresponds to the upper bound of the difference in failure rate not exceeding 0.9% if the control group failure rate is 3%. We utilized a fixed risk ratio rather than an absolute risk difference to protect against potential unexpected event rates (Head et al. 2012).

We assumed a cluster size of 900 patients (average of 150 patients per month x 6 months) and an intraclass correlation coefficient of 0.002 in the clinical outcome based on similar studies. To have 80% power to detect a risk ratio 1.3, for a one-sided hypothesis test at alpha of 0.025, we would require 19 clusters and 17,100 patients per arm (total patients n=37,620 assuming 10% loss to follow-up), rounded to a total of 40 HFs and 40,000 patients. However, due to uncertainty regarding the assumptions of the sample size calculation and to capture a wider more representative range of conditions, we will continue recruitment for Phase 1 for a minimum of 6 months.

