### 4.2 Analysis population definitions

Intention-to-treat population: This population includes all patients enrolled in the study, regardless of whether the health care worker used ePOCT+ (intervention arm), or entered the final treatment data in the eCRF (both arms).

Per-protocol population: This population only includes patients enrolled in the study for whom the clinician confirmed the final treatment (or absence of treatment) / referral status within the ePOCT+ tool (intervention arm) or in the eCRF (control arm).

Complete case set: All enrolled subjects for whom the primary endpoint of day 7 clinical cure data was collected (i.e. excluding lost to follow-up patients).

Complete consultation set: All enrolled subjects (intervention or control) for whom at least information on treatments were collected at day 0.

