## 6.2 Analysis methods

Analyses will follow CONSORT guidelines (Campbell, Piaggio, Elbourne, & Altman, 2012; Piaggio et al., 2012; Schulz, Altman, & Moher, 2010; Zwarenstein et al., 2008). Outcomes will be described by arm using summary statistics. For the non-inferiority comparison between ePOCT+ and the control arm for clinical failure, a CI approach will be used using a random effects logistic regression model using the cluster (health facility) and patient as random effects. A figure illustrating the 95% CIs of the ITT and PP relative risk of clinical failure will be presented with the pre-specified non-inferiority margin of 1.3. Non-inferiority will be achieved if the upper-bound of the RR does not surpass 1.3. If ePOCT+ is found to be

non-inferior to the control in terms of clinical failure using the PP population, then we will assess for superiority using the ITT population. Superiority will be achieved if the relative risk CI of the ITT set does not surpass 1. If clinical failure non-inferiority is established, we will test for significant differences in the co-primary outcome of antibiotic prescription rate. Since the documentation of the final treatment in both arms is part of the per protocol definition, only the PP population can be used. For this outcome, the percentage of patients receiving antibiotics at the initial consultation will also be assessed using a random effects logistic regression model with the cluster (health facility) and patient included as random effects. Binary secondary outcomes and additional analyses will be evaluated in the same way. All estimates will be reported with two-sided 95% confidence intervals (CI), except for the non-inferiority analysis which will be reported with one-sided 95% CI. The study will be deemed a success if clinical failure in the ePOCT+ arm is non-inferior to the control arm, and antibiotic prescription at the initial consultation is 25% less in the ePOCT+ arm compared to the control arm.

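### The power recalculation in SAP 3.4 that can end recruitment counts enrolled children, whereas non-inferiority is judged only in children who can be analysed, so a result at or just above 80% may overstate power

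*SAP*

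**What the plan says.** SAP 3.3 (and protocol 10.1.1) sizes the trial on day-7 clinical failure: "Assuming a failure rate (not being cured at day 7) of 3% in the control arm", a risk-ratio margin of 1.3, ICC 0.002 and 900 children per facility, "for a one-sided hypothesis test at alpha of 0.025". The result is stated as "we would require 19 clusters and 17,100 patients per arm (total patients n=37,620 assuming 10% loss to follow-up". The 10% is the only attrition allowed for.

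SAP 3.4 adds a recalculation because enrolment was low after 8 months. It updates the control-arm failure rate and the patient count, the latter by "taking into the actual enrollment numbers extrapolated up to mid-October 2022". All other parameters stay as in 3.3. If power is at least 80% the study ends in mid-October 2022; otherwise it is prolonged or facilities are added.

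SAP 6.2 moves on to superiority testing if ePOCT+ is "non-inferior to the control in terms of clinical failure using the PP population". It selects complete-case analysis for day-7 cure and cites day-7 phone loss of 13-25% in previous studies. SAP 4.2 defines PP thus: "This population only includes patients enrolled in the study for whom the clinician confirmed the final treatment" (or its absence), or the referral status, in ePOCT+ or the eCRF. Protocol 10.3 runs the non-inferiority comparison on both PP and ITT.

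**The concern.** The recalculation and the analysis refer to different sets of children. The recalculation starts from everyone enrolled and, through the unchanged parameters, removes at most 10%. The analysis removes every child without a day-7 outcome, whatever the actual rate, and in PP also every child without a confirmed treatment or referral status. Neither the observed follow-up rate nor the observed PP share enters the rule.

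The rule is binary, so the count matters most when the answer falls close to 80%. A value at or just above that line ends recruitment, while power in the analysed set may lie below it. Because the antibiotic comparison is tested only if non-inferiority is shown, lost power on clinical failure carries over to the second co-primary outcome.

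**Working it through.** **Reproducing the plan's figure.** Inputs from SAP 3.3: failure 3% in both arms, margin 0.3 × 3% = 0.9 percentage points, one-sided alpha 0.025, power 80%.

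- Individually randomised: (1.960 + 0.842)² × 2 × 0.03 × 0.97 / 0.009² = 5,640 per arm.
- Design effect: 1 + 899 × 0.002 = 2.798, giving 15,781 per arm, or 17.53 clusters of 900.
- One extra cluster per arm for the small number of clusters: 18.53, rounded up to 19, so 17,100 per arm.
- Total: 34,200 × 1.1 = 37,620.

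This matches the SAP.

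**Power formula.** With k = 20 facilities per arm, m analysed children per facility, control failure p and a true risk ratio of 1:

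- effective size per arm e = k·m / (1 + (m − 1) × 0.002)
- power = Φ(0.3p / √(2p(1 − p)/e) − 2.024), where 2.024 is the 97.5% point of t with 38 degrees of freedom.

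At p = 3% and m = 900 the same formula (with 2(k − 1) degrees of freedom) gives 79.0% at 18 clusters per arm, 81.3% at 19 and 83.3% at 20, which again points to 19.

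**Recalculation at exactly 80%.** The documents do not give the realised enrolment, so m is taken as 400 to 700 per facility after the 10% deduction. For each m, p is solved so that power is 80%; this gives p from 3.9% (m = 400) to 3.0% (m = 700). Then m is multiplied by (1 − loss)/0.9 and by the PP share, taken as equal in both arms.

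Example at m = 600, p = 3.24%, margin 0.971 percentage points:

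- m = 600: e = 12,000/2.198 = 5,460; SE = 0.339 points; 2.866 − 2.024 = 0.842; power 80.0%.
- 25% loss, m = 600 × 0.75/0.9 = 500: e = 10,000/1.998 = 5,005; SE = 0.354 points; 2.744 − 2.024 = 0.720; power 76.4%.
- 25% loss and 80% in PP, m = 400: e = 8,000/1.798 = 4,449; SE = 0.375 points; 2.587 − 2.024 = 0.563; power 71.3%.

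Over m = 400 to 700:

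| Day-7 loss | PP share | Power in analysed set |
|---|---|---|
| 10% (assumed in 3.3) | 100% | 80% |
| 13% (low end cited in 6.2) | 100% | 79% |
| 25% (high end cited in 6.2) | 100% | 76-77% |
| 10% | 95% (assumed) | 79% |
| 10% | 90% (assumed) | 78% |
| 10% | 80% (assumed) | 75-76% |
| 25% | 80% (assumed) | 70-72% |

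The last row takes the two exclusions as independent. Power falls less than the number of children does because the number of facilities is fixed.

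**Recalculation above 80%.** At a recalculated 84%, 80% in PP with 10% loss leaves 79-80%, and 25% loss with full PP leaves 80-81%. At 86% the corresponding figures are 81-82% and 82-83%; both exclusions together still leave 76-79%.

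**The case against.** **The PP share is unknown and may be high.** PP needs only the end-of-consultation entry that both arms are asked to make. Defining a PP set and reporting adherence (SAP 4.1, 4.2) does not show that many children fall outside it. This stands. The only shortfall backed by a figure in the documents comes from the 13-25% loss. Even that is from phone follow-up in earlier studies, whereas protocol 8.1.7 adds repeat calls and possible home visits.

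**The figures sit on a knife-edge.** All the main results start from exactly 80%. A reader might infer that recruitment will stop with an underpowered trial. The documents do not support that: a value clearly above 80% absorbs either exclusion alone, and one below 80% triggers prolongation anyway. At 20 facilities of 900 the formula gives 83%, and still 80% with 80% in PP.

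**The alpha is unsettled.** SAP 6.2 reports non-inferiority with a one-sided 95% CI, against the 0.025 in 3.3. At alpha 0.05 the same formula gives about 84-85% with 80% in PP at 10% loss, and 80-82% with 25% loss as well. That conflict could mask the shortfall, but it is a separate defect to reconcile and no safeguard.

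**PP may not be the sole decision set.** The PP clause in 6.2 introduces the superiority step, the sentence giving the criterion names no set, and the protocol uses both sets. This weakens any claim that PP alone decides. It does not remove the point: under the protocol's approach PP is still one of the primary sets, and complete-case analysis drops children without day-7 data from ITT too.

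**The losses may overlap.** If the same children lack both treatment entry and a day-7 outcome, the joint loss is smaller than the product used above.

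**Conclusion.** The mismatch is in the text and holds in a conditional form. If SAP 3.4 returns a value at or just above 80%, power in the analysed children can be below 80%: about 79% to 76% from the day-7 loss that the SAP itself cites, and about 70-72% if 25% loss is combined with an assumed 80% in PP. There is no gap if loss is at most 10% and treatment entry is nearly complete. These figures rest on 20 facilities per arm, ICC 0.002, one-sided alpha 0.025, a true risk ratio of 1, and a 10% deduction that is inferred from the unchanged-parameters sentence; if nothing is deducted the gap is larger.

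Two stronger readings are not supported. The mismatch does not raise the type I error, because the margin and the test do not depend on the recalculated count. Nor does it make the original sizing in 3.3 wrong: that calculation reproduces, and the stopping rule is in 3.4. It is worth correcting because the rule governs when recruitment ends and the correction is cheap.

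**What to change.** Change SAP 3.4 only. In place of the enrolment count, use: *the number of enrolled children in the per-protocol set with a known day-7 outcome, per facility, extrapolated to mid-October 2022*. Make no further 10% deduction, and apply the existing 80% rule to that number.

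The independent statistician should be given the treatment-confirmation and follow-up counts by facility; the SAP does not say that this person already holds them. No outcome by arm needs to be disclosed, so withholding the control-arm failure proportion is unaffected.

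The cost is one sentence and one data request. The downside is that the stated power may fall slightly and the existing prolongation rule may be triggered. The conflict between alpha 0.025 in 3.3 and the one-sided 95% CI in 6.2 should be settled separately, because the recalculated power depends on which one applies.

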### 3.5 Timing of final analysis

The final analysis will be performed after all subjects have the day 7 outcome measured.

## 4. Statistical principles

### 4.1 Adherence and protocol deviations

Adherence to the study protocol is assessed based on the percent of patients enrolled in the study for which the clinician entered the final treatment.

Adherence is defined as: % adherence to the study protocol = ((number of children for whom the final treatment were inputted) / (number of children enrolled in the study))\*100%

Descriptive statistics on the adherence will be provided by study arm (intervention and control)

### 4.2 Analysis population definitions

Intention-to-treat population: This population includes all patients enrolled in the study, regardless of whether the health care worker used ePOCT+ (intervention arm), or entered the final treatment data in the eCRF (both arms).

Per-protocol population: This population only includes patients enrolled in the study for whom the clinician confirmed the final treatment (or absence of treatment) / referral status within the ePOCT+ tool (intervention arm) or in the eCRF (control arm).

Complete case set: All enrolled subjects for whom the primary endpoint of day 7 clinical cure data was collected (i.e. excluding lost to follow-up patients).

Complete consultation set: All enrolled subjects (intervention or control) for whom at least information on treatments were collected at day 0.

## 5. Study population

### 5.1 Screening data

All patients presenting to the outpatient department of participating health facilities will be screened for eligibility. At the screening stage, the age of the patient and reason for coming to the health facility (acute vs. routine or chronic care visit) will be documented. The following summary data for the facility will be presented: the number of days during which screening has taken place, the number of patients recruited, the average number of patients recruited per day, the number of screened patients not recruited, and the reason for non-recruitment (e.g. non-eligibility vs. declined enrollment).

### 5.2 Eligibility

#### 5.2.1 Health facility (cluster) eligibility

Health facility eligibility for the study is based on the health facility meeting all inclusion criteria and none of the exclusion criteria:

**Inclusion Criteria:**

- Government and private government-designated Primary care HFs (health posts, dispensaries and health centers).

- Located in the Mlimba, Ifakara and Ulanga districts (Morogoro Region) or in Mbeya Rural district and Mbeya city council (Mbeya Region).
- Seeing at least 20 children aged 2 months to 5 years per week on average over the past 6 months (to facilitate participant recruitment)\*.

\*Based on estimates from extrapolated data from HMIS (MoHCDGEC-HMIS Unit)

**Exclusion Criteria:**

- Secondary and Tertiary HFs (district, regional, zonal and specialized hospitals).
- Located more than 150 km from the research institution (for feasibility considerations)

### 5.2.2 Study population eligibility

A patient is eligible for the study if they meet all inclusion criteria and none of the exclusion criteria:

**Inclusion Criteria:**

- Aged 1 day (24 hours) to 14 years (inclusive)
- Presenting for an acute medical or surgical condition

[figure not shown]
**Exclusion Criteria:**

- Presenting for scheduled consultation for a chronic disease (e.g. HIV, TB, NCD, malnutrition)
- Presenting for routine preventive care (e.g. growth monitoring, vitamin supplementation, deworming, vaccination).
- Caregiver unavailable, unable or unwilling to provide informed consent (except for older children who can provide assent with an adult witness during the consenting process).

### 5.3 Recruitment

A CONSORT flow diagram will be used to summarize the number of patients:

## 5.4 Baseline characteristics

The baseline cluster (health facility) characteristics that will be summarized by study arm include:

- Number of health facilities by type (dispensary or health center) and region
- Average number of patients seen per month by health facility type
- Availability and readiness of basic health care services score based on the Tanzanian Service Provision Assessment (median and IQR)

The baseline patient characteristics that will be summarized by study arm, and for the overall study include:

- Demographics: sex (number and percentage); age (median and IQR), age groups 0-2 months, 2 months - 5 years, 5-14 years (number and percentage)
- Medical history: Main reasons for consultation, history of fever (number and percentage)

Given the pragmatic nature of the study, and so as not to influence the normal management of patients and their outcome in the control arm, clinical signs and comorbidities will not be systematically collected in the control and intervention arm.

No formal statistical comparisons of baseline data will be performed.

## 6. Main analyses

### 6.1 Outcome definitions

#### 6.1.1 Co-primary outcomes

*1. Percentage of children cured at day 7 in the intervention group (ePOCT+) as compared to the control group (routine care)*

Outcome measure: The child is defined as being cured at day 7 if the caregiver says that the child is cured or has improved since the initial consultation. Non-referred secondary hospitalizations (if caregiver says that child was hospitalized between day 0 and day 7 but the electronic clinical data does not indicate a referral for hospitalization) will however be considered as clinical failures even if the child is already cured at day 7.

Timing and method of measurement: Assessment of subjective clinical cure by the caregiver, and history of non-referred hospitalization will be assessed by telephone or home visit follow-up 7 days (range 6-14 days) after enrollment of the subject. The day of enrollment of the subject is considered as day 0.

Analysis type: Non-inferiority.

*2. Percentage of children prescribed an antibiotic at initial consultation in the intervention group (ePOCT+) as compared to the control group (routine care)*

Outcome measure: Prescription of oral or parenteral antibiotic at initial consultation, as reported by the health care worker.

Timing and method of measurement: Documented by the health care worker at the end of the initial consultation where the subject was enrolled (day 0).

Analysis type: Superiority

#### 6.1.2 Secondary outcomes

All secondary outcomes are compared between the intervention (ePOCT+) and control (routine care) arms.

*1) Secondary consultations*

- % of children with one or more unscheduled re-attendance visits at any health facility by day 7

Timing and method of measurement: Telephone or home visit follow-up 7 days (range 6-14 days) after enrollment of the subject. The day of enrollment of the subject is considered as day 0.

*2) Severe outcome by day 7*

- % of children with non-referred secondary hospitalization by day 7
- % of children who have died by day 7

Timing and method of measurement: Death and non-referred secondary hospitalization will be assessed by telephone or home visit follow-up 7 days (range 6-14 days) after enrollment of the subject. The day of enrollment of the subject is considered as day 0.

*3) Primary referrals*

- % of children referred to hospital or inpatient ward at a health centre at initial consultation

Timing and method of measurement: Documented by the health care worker at the end of the initial consultation in the eCRF (control arm) or in ePOCT+ (intervention arm) when the subject was enrolled (day 0)

*4) Appropriate case management for malaria at initial consultation*

- % of febrile children tested for malaria by RDT and/or microscopy at day 0
- % of malaria positive children (positive RDT result OR positive microscopy result) prescribed an antimalarial at day 0
- % of malaria negative children prescribed an antimalarial at day 0
- % of untested children prescribed an antimalarial at day 0

Timing and method of measurement: Documented by the health care worker at the end of the initial consultation where the subject was enrolled (day 0)

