- ii) Medical history (questions to ask caregivers and/or children)
- iii) Physical exam (signs to look for)
- iv) POC tests (which should be performed in a given clinical context (see **Table 2**)
- v) Diagnoses
- vi) Treatments (including medicines and supportive treatments)
- vii) Counseling (explanation on final diagnoses, treatments, and follow-up)

Biosensors (presently pulse oximeter and hemoglobinometer) and rapid tests (presently malaria, HIV and semi-quantitative CRP, urine dipstick) will have to meet requirements for implementation at PHC level, including adequate measurement accuracy, stability in high-temperature and dusty settings, as well as affordability. Once adequate biosensors and POCTs are identified, manufacturer negotiations are complete, and the regulatory framework is in place, they will be used by HCWs upon recommendation provided by ePOCT+ (**Table 2**).

РОСТ	Targeted patient group	Rationale
Pulse oximetry (POX)*	Patients with respiratory complaints and severe disease Young infants with suspected severe disease	POX may improve detection of children with hypoxemia In neonates and young infants, among whom accurate respiratory rate can be difficult to ascertain and short instances of rapid breathing or apnea can be physiologic, POX may improve diagnosis and classification of severe illness
Hemoglobin (Hb)*	Patients ≤ 5 years with fever Patients 6-14 years with malnutrition, palmar pallor or conjunctival pallor	Regular Hb measurements in febrile children will improve detection of severe anemia, which is a marker of severe disease for a variety of disease pathways, including severe malaria, sickle cell disease, and severe bacterial infections
Malaria rapid diagnostic test (mRDT)	Patients with fever	Malaria is a potentially fatal disease that must be excluded in patients presenting with fever, or in a sub-group of febrile patients at high risk in very low endemic areas, as per current WHO guidelines

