Adapting the frequency of mRDT testing to malaria prevalence:

As recommended by WHO (WHO 2011), in geographical areas where the positivity rate of malaria RDT is normally or seasonally falls below 1% (based on the data gathered through the use of ePOCT+), we will modify the "fever" branch of the algorithm to target malaria testing on the patient population at risk of having malaria. To do so, we will use the combination of demographic (e.g. village where the child lives), exposure (e.g. recent travel to an endemic area) and clinical (e.g. no other documented infection) criteria shown in the data analyses to best predict the presence of malaria. In this specific geographical area, we will thus randomize (at patient level) febrile children to be managed either using the original algorithm "fever" branch (that recommends all children to be tested for malaria), or using the modified version of the "fever" branch (that targets testing to the children at risk for malaria). If we measure that the clinical cure rate is equivalent to that of children managed with the original "fever" branch, the later will be implemented for all children in that geographical area. In

case the positivity rate would later increase in that area due to resurgence of malaria, the application would revert to the original "fever" branch until malaria prevalence goes down again.

This dynamic malaria testing strategy would reduce the number of malaria tests used (that would likely have been negative) and also increase the percentage of mRDTs that are positive, which will improve the motivation and trust of HCWs in malaria testing. This strategy has already been implemented in some areas or countries in Africa using malaria predictors described in the literature, but not yet based on individual patient local data as it will be done in the present study.

Improving the accuracy of pneumonia diagnosis:

The same study design as for malaria testing will be used to improve pneumonia diagnosis accuracy using a combination of clinical predictors or new diagnostic tools, and/or to save CRP rapid tests in children with cough or difficult breathing. The new "cough" branch of the algorithm will be implemented in all children either if the clinical cure rate with the new branch is expected to be better than that of children managed with the original "cough" branch OR if the number of CRP tests used is expected to decrease.

Assessing the utility of dengue rapid tests in outbreak conditions:

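### Antimalarial prescribing is compared between arms within test-negative and untested groups formed after allocation, so a difference in testing alone can move these outcomes

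*SAP*

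**What the plan says.** SAP 6.1.2, like protocol 7.1, lists four malaria outcomes. The first is a testing rate, the percentage "of febrile children tested for malaria by RDT and/or microscopy at day 0". The other three are prescribing rates that depend on that testing. One, on under-treatment, is taken among those whose rapid test or slide was positive. Another is the percentage "of malaria negative children prescribed an antimalarial at day 0". The remaining one covers children who had no test, as the percentage "of untested children prescribed an antimalarial at day 0", and is not restricted to those with fever.

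The section opens with the rule "All secondary outcomes are compared between the intervention (ePOCT+) and control (routine care) arms". SAP 6.2 adds "Binary secondary outcomes and additional analyses will be evaluated in the same way", meaning the random effects logistic model used for the antibiotic co-primary. It says nothing about denominators that may differ by arm.

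The definitions in SAP 6.1.2 make malaria testing an order by the health worker at the visit. Protocol 8.2 describes the original ePOCT+ fever branch as one "that recommends all children to be tested for malaria". Table 2 in protocol 6.1 assigns the rapid test to patients with fever on the ground that "Malaria is a potentially fatal disease that must be excluded in patients presenting with fever", and goes on to allow a narrower high-risk group in very low endemic areas.

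Neither the secondary outcomes nor the exploratory analyses in SAP 6.3 include antimalarial use over all children or over all febrile children. Protocol 8.1.7 shows that tests, results and treatments are recorded in both arms.

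**The concern.** Randomisation makes the arms comparable over all enrolled children. It does not make them comparable within groups defined by a later decision that the intervention sets out to change. If ePOCT+ leads to more testing, children under low suspicion of malaria move out of the untested group and into the test-negative group. The conditional rates then change even if nobody treats any type of child differently.

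The test-negative and untested rates are the two outcomes that speak to over-treatment. The test-positive rate speaks to under-treatment. It is exposed to the same shift in principle, but no figure is offered for it here.

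The untested outcome is the weakest because it is not limited to febrile children. As febrile children are tested, the group that remains is increasingly non-febrile and unlikely to be treated for malaria.

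Covariate adjustment is unlikely to repair this. SAP 6.2 adjusts for baseline imbalance between study groups, not within test-defined subsets, and SAP 5.4 says that clinical signs and comorbidities are not collected systematically. The level of suspicion that drives testing is therefore largely unmeasured. Rational antimalarial use is part of what the secondary outcomes are meant to show (protocol synopsis, procedures for Objective 1), so a case-mix effect could be reported as better prescribing.

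**Working it through.** The documents give no testing rate, positivity or antimalarial rate for either arm, so there is no figure of the plan's own to reproduce. Every rate below is an assumption. Over-treatment means an antimalarial given without a positive test, whether the child tested negative or was not tested.

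**1. Untested outcome, with no prescribing rate changed.** Take 1,000 children per arm: 600 febrile and 400 non-febrile, only febrile children tested, 10% positivity, 10% of test-negative and of untested febrile children treated, 0% of non-febrile children treated. With a share t of febrile children tested:

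- test-negative = 600 × t × 0.9
- untested febrile = 600 × (1 − t)
- untested rate = 0.10 × 600 × (1 − t) / (1,000 − 600t)
- over-treatment = 0.10 × (test-negative + untested febrile) / 1,000

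| Febrile children tested | Test-negative | Untested (of whom febrile) | Untested outcome | Over-treatment, all children |
|---|---|---|---|---|
| 50% | 270 | 700 (300) | 30/700 = 4.3% | (27 + 30)/1,000 = 5.7% |
| 70% | 378 | 580 (180) | 18/580 = 3.1% | (37.8 + 18)/1,000 = 5.6% |
| 90% | 486 | 460 (60) | 6/460 = 1.3% | (48.6 + 6)/1,000 = 5.5% |
| 95% | 513 | 430 (30) | 3/430 = 0.7% | (51.3 + 3)/1,000 = 5.4% |

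With ePOCT+ at 95% and control at 50%, the listed outcome falls about sixfold and over-treatment hardly moves. With control at 90%, the artefact is 1.3% v 0.7%.

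**2. Test-negative outcome, with identical behaviour by level of suspicion.** Take 100 febrile children, half strongly suspected, and positives few enough to ignore. Both arms treat 20% of strongly suspected and 2% of low-suspicion children, tested or not.

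- Control tests only the strongly suspected. The test-negative rate is 10/50 = 20%. Over-treatment is 50 × 20% + 50 × 2% = 11 per 100.
- ePOCT+ tests all. The test-negative rate is (10 + 1)/100 = 11%. Over-treatment is 11 per 100.

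The listed outcome shows a relative fall of 1 − 11/20 = 45% with no difference in behaviour. If control also tested a share g of low-suspicion children, its rate would be (10 + g)/(50 + 50g). That is 14% at g = 0.5 (75% tested overall) and 12% at g = 0.8 (90% tested).

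**3. Can over-treatment rise while every listed outcome improves?** Moving one febrile child from untested to tested changes the chance of over-treatment from u, the rate in untested febrile children, to (1 − p) × n, with p the positivity and n the rate in test-negatives. When the rates themselves also fall, a rise needs (1 − p) × n above u in the control arm and a large enough testing gap.

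- Possible: keep 60% febrile, 10% positivity and testing of 50% v 95%. Let the rate in test-negatives fall from 15% to 12%, the rate in test-positives rise from 90% to 95%, and u be 5%. The untested outcome falls from 15/700 = 2.1% to 1.5/430 = 0.35%. Over-treatment rises from (40.5 + 15)/1,000 = 5.55% to (61.56 + 1.5)/1,000 = 6.31%.
- Opposite: let the rate in test-negatives fall from 5% to 4%, with u at 30%. Over-treatment falls from (13.5 + 90)/1,000 = 10.35% to (20.52 + 9)/1,000 = 2.95%.

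A grid of 1,000 assumed settings had control testing of 30% to 95% against 95%, positivity 2% to 20%, rates of 2% to 20% in negatives, 2% to 30% in untested febrile and 0% to 1% in untested non-febrile children, with these prescribing rates 10% lower in relative terms under ePOCT+. Over-treatment rose in 202. Where (1 − p) × n exceeded u, it rose in 72, 70, 60, 0 and 0 of 72 settings at control testing of 30%, 50%, 70%, 90% and 95%. It rose in none of the other 640.

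**The case against.** The strongest reply is that a large testing gap is assumed, not documented. By the footnote to Table 2 in protocol 6.1, the malaria rapid test is routine and not supplied by the project. Control staff receive paper guidelines and are reminded to follow them, and ePOCT+ users may override the tool (protocol 8.1.6). SAP 3.1 promises the control arm equivalent clinical training. This stands: if control testing is already near 90%, the distortion is small.

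A second reply is that the testing rate is reported beside the three conditional rates, so a shift would be visible, and that those rates answer a fair question, namely whether staff act on the result. This also stands, but seeing a shift does not correct for it, and the SAP treats the rates as ordinary between-arm comparisons.

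A reader might infer from example 2 that over-treatment rises under ePOCT+, since children treated despite a negative test go from 10 to 11 per 100. That count leaves out the control arm's untested children. At the same 2% they add 1, and the totals are equal. Nor is a zero rate in untested children a neutral assumption: protocol 1.2 says that staff sometimes give antimalarials out of caution.

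Finally, a denominator of children with day-0 treatment data is not strictly fixed at allocation, because it needs a completed entry (SAP 4.2). This is true, but membership does not depend on whether the child was tested.

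**Conclusion.** The point holds as one of comparability. The between-arm comparisons in test-negative and untested children, and in test-positive children for under-treatment, rest on groups formed after allocation by a decision that ePOCT+ targets. No outcome on a denominator independent of testing is listed to set beside them. Under the stated assumptions, a testing difference alone can produce 4.3% v 0.7% in untested children, or 20% v 11% in test-negative children, with over-treatment unchanged or nearly so.

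The documents do not support the stronger reading that these outcomes will improve while over-treatment rises. That is possible on assumed rates (5.55% to 6.31%), but it needs a sizeable testing gap and test-negative children treated often enough relative to untested febrile children. The size and direction in this trial are unknown. None of these outcomes enters the success criterion in SAP 6.2, so the consequence is limited to what is claimed about antimalarial use.

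**What to change.** In SAP 6.1.2, add one outcome compared between arms with the same model: the percentage prescribed an antimalarial at day 0 without a positive test, counting negative and untested children together. Give it over all children with day-0 treatment data, and over those with a history of fever, which SAP 5.4 already lists as a baseline characteristic by arm.

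Report the three conditional rates as descriptive, with their denominators, next to the percentage tested and the percentage test-positive. Split the untested rate by history of fever.

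Do not add, as a between-arm outcome, the percentage of all children who test positive and are not prescribed an antimalarial, because it rises mechanically with testing. Assuming 10% positivity and 10% of positives untreated in both arms, 50 tested per 100 gives 50 × 0.1 × 0.1 = 0.5 per 100, and 100 tested gives 1.0.

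The cost is SAP wording; the fields are already captured. The drawback is that the new percentages are smaller and less comparable with routine programme indicators, which is why the conditional rates should stay in the report.
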